2.1 Background & Aims

Osteoarthritis is a degenerative joint disease-causing joint pain, stiffness, and functional limitations due to progressive cartilage damage, structural changes, and synovial proliferation. OA prevalence is higher in women, with knee being the most affected joint, with 344 million people suffering from mild to severe osteoarthritis potentially benefiting from rehabilitation. A study in India found a significant difference in knee joint arthritis prevalence between rural (56.6%) and urban (32.6%) areas, with Asians having a higher risk. Kinesio phobia, or the fear of movement, has been linked to a number of illnesses, including shoulder pain, chronic low back pain, and chronic fatigue syndrome. Direct experiences or social learning have been found to have an impact on learning.

Deep breathing promotes calmness, emotional control, deeper thinking, and better metabolism, while shallow thinking can lead to impulsive behaviour, rapid breathing, and mistakes. Yoga is a mind-body therapy that combines physical and mental practice through postures and breathing, enhancing balance, strength, flexibility, and endurance through both upper and lower extremities. Exercise and physiotherapy treat knee osteoarthritis for nearly a century, second most prescribed treatment after oral medicine. Patients should exercise alone, at home, or in class.

By combining conventional physiotherapy with relaxation techniques like deep breathing technique and three typical yoga postures, our method not only helps people with Kinesio phobia but also improves their knee range of motion, balance, and coordination so they can actively resume their daily lives.

2.2 Background Literature Review

- **Subha Pragathi Kanniappan et al (2021)** concluded that people with OA knee experience increased levels of Kinesio phobia when their pain intensity increases in tandem with the evolution of their OA stage or degree. Disability, a lower quality of life, a decrease in exercise tolerance, and dependence are all possible outcomes of this. A crucial component of evaluation for improved rehabilitation results is determining the degree of Kinesio phobia.
- **[name] et al (2012)** The findings imply that breathing patterns have a significant impact on autonomic and pain processing. They could expand on recent research that found DSB and relaxation to be crucial components in the regulation of sympathetic arousal and pain perception, based on an experimental study methodology.
- **Elizabeth Whissell et al (2021)** proposed suggested that the motion patterns of the lunge and warrior II poses were comparable in terms of angular impulse, joint angles, and joint moments. Compared to the other two maneuvers, the triangle position may be better since it increases hip joint range of motion, strength, and dynamic stability.
- **Michael Langworthy et al (2024)** concluded that OAK is a common illness that causes a significant economic and humanistic burden due to its varied disease presentation and course. Although there are currently no known disease modifying treatments, a number of nonsurgical alternatives have been described. However, treatments that can significantly reduce pain and enhance functional outcomes are still needed. There is potential to better control pain and improve mobility thanks to recently developed therapy methods.
- **Tampa scale:**
In (2023) **Frederique Det al**, the Clinical Journal of Pain published a thorough systematic study that looked into the TSK's psychometric qualities in people with musculoskeletal pain. The purpose of the study was to determine the validity and reliability of various TSK

versions. The results demonstrated the TSK's reliability as a Kinesio phobia test in this demographic.

- **Visual Analog scale:**

VAS design, widely used in health condition appraisals, has been subject to variations in scale length and endpoint descriptors, making cross-study comparisons challenging. To improve comparability and reliability, standardization in VAS application is essential, as revealed by **Mimmi Astrom et al (2023)** scoping assessment.

- **Short-form McGill Pain Questionnaire (SF-MPQ-2):**

Jumbo et al. (2020) study examined the SF-MPQ-2's repeatability in individuals with musculoskeletal shoulder discomfort. Internal consistency and test-retest reliability of the questionnaire were evaluated. According to the results, the SF-MPQ-2 is a valid tool for assessing pain in this patient group, hence facilitating its application in both clinical and research contexts.

3. Study Protocol

3.1 Research Design Outline

The study aims to perform a comparative study on Knee Osteoarthritis with Kinesio phobia in Saveetha Medical Hospital.

Formerly titled “Effectiveness of Deep Breathing and Three Typical Yoga Poses for Kinesiophobia among Knee Osteoarthritis patients: A Comparative Study” involves documented diagnosis of knee osteoarthritis patients with Kinesio phobia. The three main outcomes that will be measured were Tampa scale, Visual analogue scale and short form McGill Pain Questionnaire (SF-MPQ 2).

3.2 Participants

Older aged patients from Saveetha Medical Hospital with Knee Osteoarthritis along with kinesiophobia will be eligible to participate in this study.

3.3 Recruitment

All Elderly patients with Knee Osteoarthritis along with Kinesio phobia will be enrolled in the comparative study. The patient's information and consent sheet will be distributed to patients which details including inclusion and exclusion criteria. Patients who agree to the investigation will be invited to undergo baseline assessments Tampa scale, Visual Analog scale, Short-form McGill Pain Questionnaire (SF-MPQ-2). All the patients will have to return a signed consent form to the site principal investigator.

3.4 Administration

For Deep Breathing:

The patients will be seated on chairs and will be given a 3-minute, 6 deep breaths per minute session along with the CP protocol 5 times a week for 3 weeks.

For yoga:

The steps with yoga mat include;

Due to the considerable knee extensor and adductor moments, attention should be paid throughout performance.

1.Crescent lunge pose:

- Begin by assuming the downward-facing dog pose.

- Take a breath, lift your right leg behind you, and then step your right foot forwards between your palms.
- Verify that the right ankle is in line with the right knee.

2. Warrior II pose:

- Start in mountain pose (Tadasana).
- Step your left foot back
- Extend your arms out.
- Position your hips
- Bend deeply into the right knee
- Gaze directly above your right middle finger
- Breathe, hold, and strengthen
- Step back into mountain pose

3. Triangle pose:

- Hold the position with your knees and elbows straight.
- Inhale. Raise your right hand straight above your head, parallel to your right ear.
- Take a breath. Bend your torso at the waist, to your left side.
- At the same time, slide your left arm down along your left leg until your fingers are at your ankle.
- Keep your head tilted to the left at this point.
- Inhale. Straighten yourself and stand erect. Repeat the pose on the other side.

For Conventional Physiotherapy:

- The exercises are intended to strengthen, stretch, and stabilise the knee's supporting tissues. Exercise protocol follows for 1 time a day, 5 days per week for 4 weeks.

1. Straight-leg raise (sitting):

- Maintain proper posture when sitting comfortably on the chair. One leg should be straightened, held for a slow count of ten, and then gently lowered.
- Repeat this at least 10 times with each leg.

2. Quadriceps stretch:

- While lying down, perform this at least once per day. Under the ankle of the leg that has to be worked, place a rolled-up towel.
- At the knee, bend the opposite leg. Firmly press the rear of your knee towards the floor or bed using the muscles in your straight leg.
- Hold for five slow counts. With each leg, repeat at least five times.

3. Hamstring stretch:

- Stretch your legs out in front of you while sitting on the floor.
- Bend one knee slowly while keeping your foot flat on the floor until it feels pleasantly stretched.
- Hold for five seconds. For five seconds, hold your leg as straight as possible. Do this ten times for per leg.
- Sitting on a sofa, move your foot along a board or tea tray if you are unable to reach the floor.

4. Knee squats:

- Grasp a chair or work surface for stability.
- Make sure your kneecap covers your big toe by squatting down.
- Go back to standing. Do this ten times or more.
- Aim for a little deeper squat as you get better.

- Keep your knees bent at a proper angle at all times.

3.5. Primary outcomes

Tampa scale:

The Tampa scale will initially be used to distinguish between non-excessive fear and phobia in patients with chronic musculoskeletal pain, i.e., the fear of movement. In its original form, the TSK will be a 17-item assessment checklist. It will use a 4-point Likert scale (Strongly Disagree-Disagree-Agree-Strongly Agree) with statements that will later be linked to the model of fear-avoidance, fear of work-related activities, fear of movement, and fear of re-injury.

Visual Analogue Scale (VAS):

The Visual Analogue Scale (VAS) is a widely used tool for measuring pain severity, with endpoints ranging from "no pain" to "worst pain imaginable." Patients mark points on the scale, and clinicians track changes over time. The VAS has been shown to have high internal consistency, with Cronbach's alpha coefficients ranging from 0.71 to 0.95. The VAS has been shown to have good construct validity, correlating with other measures of pain intensity, such as the Numerical Rating Scale (NRS) and the McGill Pain Questionnaire (MPQ).

Short-form McGill Pain Questionnaire (SF-MPQ-2):

The Short Form McGill Pain Questionnaire 2 (SF-MPQ-2) is a modified version of the original SF-MPQ, assessing pain in patients with various conditions. It comprises 22 descriptors rated on a 0-10 scale, providing a comprehensive evaluation of pain. The

SF-MPQ-2 has demonstrated strong internal validity. A 2020 systematic review published in the Annals of the Rheumatic Diseases found that the SF-MPQ-2 has good internal consistency, with Cronbach's alpha values ranging from 0.77 to 0.92.

4. Statistical Analysis Plan (SAP)

Descriptive and inferential statistics will be used. Normally distributed data will be presented by mean and standard deviation (SD), and non-normally distributed data will be presented by median and interquartile range. SPSS (version 22.0) will be used for all statistical analyses.

4.1 Primary Outcomes

The primary analyses will compare experimental vs control group guidelines on their mean and standard deviation: (i)Tampa scale, (ii) Visual Analogue Scale (VAS), (iii) Short-form McGill Pain Questionnaire (SF-MPQ-2) Comparison will be tested by using the Paired t test to find the significant difference within the intervention effects and between the two groups (Experimental control group and Experimental Group) using independent t-test. P values <0.05 has been considered statistically significant.

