4.2 Missing Data

For patients who do not attend the assessment, the mean imputation of the assessment scores from their allocation group has been used.

5. Informed Consent Forms (ICF)

Written consent will be gained from the patients with Knee osteoarthritis along with Kinesio phobia using the consent forms attached to the application.

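### Section 4.1 names experimental versus control as the primary contrast but tests it partly with within-arm paired t-tests at the same P<0.05

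*SAP*

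**What the plan says.** Under the heading for primary outcomes, section 4.1 first fixes the contrast: "The primary analyses will compare experimental vs control group guidelines on their mean and standard deviation", for the Tampa scale, the VAS and the SF-MPQ-2. The next sentence gives the tests: "Comparison will be tested by using the Paired t test to find the significant difference within the intervention effects and between the two groups". That sentence then assigns the group comparison its own test: "between the two groups (Experimental control group and Experimental Group) using independent t-test". A single 0.05 threshold follows and covers all of them.

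Section 3.1 gives the aim as comparative: "The study aims to perform a comparative study on Knee Osteoarthritis with Kinesio phobia". On background treatment, section 2.1 describes the method as "By combining conventional physiotherapy with relaxation techniques like deep breathing technique and three typical yoga postures", and section 3.4 schedules the breathing sessions as "6 deep breaths per minute session along with the CP protocol 5 times a week for 3 weeks".

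No section labels the paired tests secondary, supportive or descriptive, and none says which test decides effectiveness.

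**The concern.** A paired t-test within one arm has no control term. It asks whether that arm changed, not whether it changed more than the other. In this programme an arm can change because of natural course or because of the physiotherapy given with the breathing, even if breathing and yoga add nothing. Section 4.1 nevertheless places the paired test inside the primary analysis and describes the within-arm change as an effect of the intervention.

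At stake is which result carries the conclusion. Suppose the experimental arm improves significantly from baseline and the between-group test on the same scale shows no difference. The plan then holds two primary results that point different ways and has no rule for choosing between them. The SAP does not say the before-after result would be reported as effectiveness, but nothing in section 4.1 prevents it.

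**Working it through.** **What each test estimates.** Let the mean change be δ_E in the experimental arm and δ_C in the control arm.

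- Paired t-test, experimental arm: null hypothesis δ_E = 0.
- Independent t-test on change: null hypothesis δ_E − δ_C = 0. On follow-up scores it targets the same difference if the arms have equal expected baselines.

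If both arms change by the same amount δ ≠ 0, the first null is false and the second is true. The paired test should then reject more often than 5%. That rejection is correct as evidence of change and says nothing about experimental versus control.

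**Inputs.** The 0.05 level comes from section 4.1; two-sided testing is assumed. The SAP gives no sample size, SD or effect size, so there is no figure of the plan's own to reproduce. The following are assumptions for illustration: 20 or 30 per arm; complete data; normal scores; no difference between arms; a common true change of d_z = 0.2 to 0.5, where d_z is mean change divided by SD of change; baseline-to-follow-up correlation 0.5 or 0.8.

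**Step 1: how often the experimental arm's paired test is significant.** Power is P(|T| > t_crit), where T is noncentral t with n − 1 degrees of freedom and noncentrality d_z√n. The critical value is 2.093 for n = 20 and 2.045 for n = 30. For example, n = 20 and d_z = 0.2 gives noncentrality 0.2 × √20 = 0.894 and power 0.136. At n = 30 and d_z = 0.5 it is 0.5 × √30 = 2.739, with power 0.754.

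| d_z | n = 20 per arm | n = 30 per arm |
|---|---|---|
| 0.2 | 0.136 | 0.185 |
| 0.3 | 0.247 | 0.355 |
| 0.4 | 0.397 | 0.563 |
| 0.5 | 0.565 | 0.754 |

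**Step 2: significant in the experimental arm, not in the control arm.** The arms are independent, so this is p(1 − p).

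- n = 20, d_z = 0.2: 0.136 × 0.864 = 0.118
- n = 20, d_z = 0.5: 0.565 × 0.435 = 0.246
- n = 30, d_z = 0.4: 0.563 × 0.437 = 0.246
- n = 30, d_z = 0.5: 0.754 × 0.246 = 0.185

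The range is about 12% to 25%.

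**Step 3: paired test significant, independent t-test not.** This was simulated with 50,000 trials per setting (Monte Carlo standard error at most 0.002).

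- Independent test on follow-up scores: 0.127 to 0.717
- Independent test on change: 0.115 to 0.724

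**Step 4: the independent t-test alone.** In the same simulations it rejects in 0.047 to 0.052 of trials on follow-up scores and 0.048 to 0.051 on change, which is the nominal 5%. With d_z = 0, the paired test also rejects in about 5%. The gap in Steps 1 to 3 therefore comes entirely from the shared change from baseline.

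**Left out.** Regression to the mean on the Tampa scale could add to a before-after change if patients were selected on the baseline score itself, and would add nothing if selection used a separate earlier score. No size is claimed for it. The 5% in Step 4 is for complete data; the effect of the group-mean imputation in section 4.2 on that test is a separate matter.

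**The case against.** The sentence is clumsy, and its natural reading is conventional: paired test for change within an arm, independent test between arms. On that reading each test answers its own question. The only sentence that uses the term primary analyses attaches it to experimental versus control, and that contrast has a suitable test. The harm depends on how results are later reported, and no success rule is tied to a paired test. The percentages are mostly the power of a paired test to detect a change that was assumed to be real, so they depend on the chosen inputs and are not error rates of this plan.

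Much of this stands. The conventional reading is accepted here, a valid between-group test is present, and the percentages show only the mechanism.

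The objection does not remove the problem. Even on the conventional reading, the paired tests sit in the primary section, serve the same stated comparison, share its threshold and credit before-after change to the intervention. No other section demotes them. Fixing in advance which result carries the conclusion is a core purpose of an analysis plan, so this cannot be left to the reporting stage.

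**Conclusion.** The concern holds. Section 4.1 gives within-arm paired tests the same standing as the between-group test for a contrast that only the latter can address. The primary analysis is not missing, but the test that decides effectiveness is not fixed. This should be corrected.

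Under the stated assumptions, a trial with no difference between arms shows a significant before-after change in the experimental arm 14% to 75% of the time. It shows that change without a significant between-group difference about 12% to 72% of the time. The between-group test rejects in about 5%. Other sample sizes or amounts of change would move the first two ranges. Confidence in the textual point is high; the percentages are not estimates for this trial.

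**What to change.** In section 4.1, state that conclusions on effectiveness rest only on the between-group comparison. Move the paired results out of the primary analysis and label them as description of change, for example mean change in each arm with a 95% confidence interval.

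This changes SAP wording only and needs no new data, visits or patients. The downside is that before-after P values no longer count as evidence of effect. The change does not settle multiplicity across the three outcomes, which is a different question.

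### The between-group primary test is an unadjusted independent t-test although baseline scores on all three scales are collected, which loses precision and leaves baseline imbalance without proper correction

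*SAP*

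**What the plan says.** Section 3.1 names the outcomes: "The three main outcomes that will be measured were Tampa scale, Visual analogue scale and short form McGill Pain Questionnaire (SF-MPQ 2"). Section 3.3 plans a baseline measurement of each, since consenting patients are "invited to undergo baseline assessments Tampa scale, Visual Analog scale, Short-form McGill Pain Questionnaire (SF-MPQ-2").

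Section 4.1 contains the whole primary analysis. Within groups: "Comparison will be tested by using the Paired t test to find the significant difference within the intervention effects". Between groups, the comparison is made "between the two groups (Experimental control group and Experimental Group) using independent t-test". The criterion is "P values <0.05 has been considered statistically significant".

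The SAP nowhere names a covariate, ANCOVA or any other baseline adjustment of the between-group comparison. Nor does it say whether the independent t-test is applied to follow-up scores or to change from baseline.

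**The concern.** The baseline value of the same scale is usually a strong predictor of the follow-up score. This trial plans to measure it for all three primary outcomes and then leaves it out of the model for the between-group comparison. The paired t-test does not fill the gap: it uses baseline only inside each arm and says nothing about the difference between arms.

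Two things are at stake.

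- **Precision.** The unadjusted test leaves in the error term variation that baseline would explain, so the trial has less power than its data allow.
- **Baseline imbalance.** In a small trial the arms can differ at baseline by chance. A follow-up comparison passes part of that difference into the treatment estimate. A change-score comparison subtracts too much of it, which favours the arm with the worse starting scores.

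Because section 4.1 leaves the choice between follow-up and change scores open, even the direction of the distortion is not fixed in advance.

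**Working it through.** **Inputs.** From the SAP: three primary outcomes, each with a planned baseline score (3.1, 3.3); an unadjusted independent t-test; significance level 0.05 (4.1). The SAP states no sample size, power, SD, effect size or correlation, so it has no figure to reproduce. Everything below rests on these assumptions: equal SD at both visits, a two-sided test, 1:1 allocation, a baseline-to-follow-up correlation ρ of 0.3 to 0.8, a true difference of 0.6 SD, and 15 to 30 patients per arm.

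**Step 1: variance of the between-group estimate, relative to follow-up scores.**

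- t-test on follow-up scores: 1
- t-test on change scores: 2(1 − ρ)
- ANCOVA: 1 − ρ²

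| ρ | Follow-up | Change | ANCOVA | ANCOVA ÷ change |
|---|---|---|---|---|
| 0.3 | 1 | 1.40 | 0.91 | 0.65 |
| 0.5 | 1 | 1.00 | 0.75 | 0.75 |
| 0.7 | 1 | 0.60 | 0.51 | 0.85 |
| 0.8 | 1 | 0.40 | 0.36 | 0.90 |

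The ordering does not depend on the assumed ρ. For any ρ strictly between 0 and 1, 1 − ρ² is below 1. Also (1 − ρ²) ÷ 2(1 − ρ) = (1 + ρ)/2, which is below 1. At ρ = 0.5, a relative variance of 0.75 is worth 1/0.75 = 1.33, or 33% more patients, against either t-test.

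**Step 2: power.** Noncentral t, two-sided 0.05, difference 0.6 SD, with one degree of freedom deducted for ANCOVA:

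| Per arm | ρ | Follow-up t-test | Change t-test | ANCOVA |
|---|---|---|---|---|
| 30 | 0.3 | 0.628 | 0.489 | 0.668 |
| 30 | 0.5 | 0.628 | 0.628 | 0.751 |
| 30 | 0.7 | 0.628 | 0.839 | 0.892 |
| 20 | 0.5 | 0.456 | 0.456 | 0.569 |

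**Step 3: how often imbalance arises.** Under random allocation the baseline difference has standard error √(2/n) SD. The chance that it exceeds 0.3 SD in either direction is 2[1 − Φ(0.3/√(2/n))]:

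- n = 15: 0.3/0.365 = 0.82, chance 0.411
- n = 20: 0.3/0.316 = 0.95, chance 0.343
- n = 30: 0.3/0.258 = 1.16, chance 0.245

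**Step 4: what a 0.3 SD imbalance does to the estimate.** Follow-up scores shift by ρ × 0.3; change scores shift the opposite way by (1 − ρ) × 0.3.

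| ρ | Follow-up shift (SD) | Change shift (SD) |
|---|---|---|
| 0.3 | +0.09 | −0.21 |
| 0.5 | +0.15 | −0.15 |
| 0.7 | +0.21 | −0.09 |

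Under a linear relation between baseline and follow-up, ANCOVA removes the shift.

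**The case against.** The strongest reply is that the planned test is not invalid. If allocation is random, an independent t-test on either score is unbiased on average and holds its type I error. That stands: this is an inefficient choice, not an erroneous one, and no inflation of the false-positive rate is claimed.

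Second, the size is assumed. The gain can be modest: at ρ = 0.3 it is 9% of the variance against follow-up scores (power 0.628 to 0.668), and at ρ = 0.8 it is 10% against change scores. This also stands, but the two weak cases do not coincide. Where the gain over one score is small, the gain over the other is large (35% against change scores at ρ = 0.3, 64% against follow-up scores at ρ = 0.8).

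Third, section 3.3 only invites patients to the baseline assessments, and section 4.2 imputes the allocation-group mean for patients who miss the assessment. Imputed follow-up scores would weaken the observed correlation and so reduce the achievable gain below the figures shown. That is a fair caution about size and does not favour the unadjusted test.

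Fourth, the SAP does not describe how patients are allocated, which may be in the protocol. Without random allocation, ANCOVA and change scores can estimate different things, and ANCOVA need not remove all the bias. True, but baseline differences then matter more, and an unadjusted t-test offers no protection against them.

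**Conclusion.** The concern holds. Section 4.1 fixes a between-group test without baseline adjustment while section 3.3 plans the baseline scores that would allow it. The direction is certain for any correlation between 0 and 1; the amount is not, because the SAP gives none of the quantities needed.

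Over assumed correlations of 0.3 to 0.8, ANCOVA lowers the variance by 9% to 64% against follow-up scores and by 35% to 10% against change scores. At the sizes considered, 15 to 30 per arm, a baseline difference above 0.3 SD would occur by chance in about 41% to 25% of trials and would move an unadjusted estimate by 0.09 to 0.21 SD for correlations of 0.3 to 0.7.

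This is a change that should be made; it is not a flaw that invalidates the analysis.

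**What to change.** In section 4.1, replace the independent t-test for each of the three scales with a linear model (ANCOVA) of the follow-up score on arm, with the baseline score of the same scale as covariate. Report the adjusted mean difference with its 95% confidence interval and P value. State in the same place which assessment supplies the follow-up score. The within-group paired tests can stay as description but should not be read as evidence of a difference between arms.

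This also settles the open choice between follow-up and change scores before the data are seen. The cost is a change of SAP wording and one degree of freedom per model. It needs no new data, and the analysis is standard in SPSS, the package the SAP already names.

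### Three equal primary scales are each tested at P<0.05 with no rule for success; if any one scale is enough, the false-positive rate is about 8–14%

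*SAP*

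**What the plan says.** Section 3.1 puts the three scales on one footing: "The three main outcomes that will be measured were Tampa scale, Visual analogue scale and short form McGill Pain Questionnaire (SF-MPQ 2"). Section 3.5 describes all three under its heading of primary outcomes, and section 4.1 lists them as (i), (ii) and (iii) within the primary analyses.

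Section 4.1 names two kinds of test. For change within a group: "Comparison will be tested by using the Paired t test to find the significant difference within the intervention effects". For the comparison of groups: "between the two groups (Experimental control group and Experimental Group) using independent t-test". One threshold then covers everything: "P values <0.05 has been considered statistically significant".

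The SAP does not rank the scales, order the tests, adjust the threshold, or say how three primary results combine into one conclusion.

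**The concern.** With three primary tests, a 0.05 threshold for each does not fix the error rate of the trial's conclusion. That depends on the rule joining the tests, and the rule is absent. A claim based on whichever scale is significant is compatible with section 4.1 as written, and so is a claim that requires all three. The two have very different error rates, and the choice between them can be made once the results are known.

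The scales also measure different things. The study title in section 3.1 concerns effectiveness for kinesiophobia. Only the Tampa scale measures fear of movement; VAS and SF-MPQ-2 both measure pain. The plan would allow a positive primary claim resting on a pain scale with no effect on kinesiophobia.

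The paired tests add a further route. They sit in the same primary section under the same threshold and are not marked as descriptive. A change within one group does not compare the treatments, so improvement in both groups could be read as effectiveness.

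**Working it through.** The SAP states no familywise error rate, so there is no figure of its own to reproduce.

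**Inputs**

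- Threshold 0.05 per test (section 4.1). Sidedness is not stated; two-sided is assumed, so the critical value is 1.96.
- Three between-group primary tests (sections 3.1, 3.5 and 4.1).
- Correlation between scales: no figure is given. Section 3.5 says only that VAS is known for "correlating with other measures of pain intensity, such as the Numerical Rating Scale (NRS) and the McGill Pain Questionnaire (MPQ"). A range of 0 to 0.9 is therefore assumed.

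**Any one of three, independent scales**

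1 − 0.95³ = 1 − 0.8574 = 0.1426, or 14.3%. The upper bound under any dependence is 3 × 0.05 = 15.0%.

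**Any one of three, common correlation r**

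The probability that at least one |Z| exceeds 1.96, with no true effect on any scale, by numerical integration over a shared factor:

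| r | Familywise error |
|---|---|
| 0 | 14.3% |
| 0.3 | 13.6% |
| 0.5 | 12.5% |
| 0.7 | 10.9% |
| 0.8 | 9.8% |
| 0.9 | 8.4% |

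Simulated two-sample t-tests with an assumed 15 or 30 patients per group agree: 13.6–13.7% at r = 0.3 and 9.8–10.0% at r = 0.8.

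**Any one of three, pain scales more closely related to each other**

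| Tampa–pain r | VAS–SF-MPQ-2 r | Familywise error |
|---|---|---|
| 0.2 | 0.6 | 13.2% |
| 0.2 | 0.8 | 12.3% |
| 0.5 | 0.6 | 12.3% |
| 0.5 | 0.8 | 11.5% |

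**Either pain scale, ignoring the Tampa scale**

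1 − 0.95² = 9.75% if independent, falling to 7.0% at r = 0.9. At the assumed 0.6–0.8 for this pair it is 8.8–7.8%.

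**All three required**

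The error cannot exceed the 5% of a single test, so no adjustment is needed.

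These figures cover the three between-group tests only. The paired tests are not counted; treating them as evidence of effect would add further chances of a false claim.

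**The case against.** The strongest reply is that the inflation is conditional. Section 4.1 sets a threshold for each test and never says that one significant scale makes the trial positive. What the text shows is a missing rule, not an inflated error rate. That is correct, and the figures above are stated on that condition. It does not remove the defect: the condition is left open in the section that fixes the primary tests and their threshold, which is where it should be settled. An unseen protocol does not excuse that.

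Second, the title points to kinesiophobia and the Tampa scale is always listed first, so a lead outcome might be inferred. This supports putting the Tampa scale first in a revised plan, but it is not a declared hierarchy, since sections 3.1, 3.5 and 4.1 present all three as main or primary.

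Third, the ends of the 8–14% range need every correlation to be 0.9 or 0. Neither is likely: section 3.5 argues against zero between VAS and the McGill questionnaire, and nothing supports 0.9 between fear and pain. This stands; the ends are extremes and 11.5–13.2% is the more plausible part of the range.

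Fourth, a real effect on pain alone would not be a false positive. This also stands. It is a question of what the trial may claim, separate from the familywise figures, which assume no effect on any scale. A stated order of testing settles both.

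Finally, section 4.1 opens with the comparison of groups, so the paired tests can be seen as secondary. The text does not say so, and one sentence would make it clear.

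**Conclusion.** The concern holds and should be corrected before group results are seen. The SAP has three equal primary outcomes, each tested at 0.05, and no rule for what counts as success. If any one scale suffices, the familywise error is above the nominal 5% at every correlation considered: 14.3% at r = 0 down to 8.4% at r = 0.9, and 11.5–13.2% under the mixed correlations assumed above. This rests on two-sided tests, no true effect on any scale, and assumed correlations. If all three scales were required, there would be no inflation.

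**What to change.** Amend section 4.1, before group results are seen, to state:

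1. The confirmatory tests are the between-group comparisons, in fixed order: Tampa scale at two-sided 0.05, then VAS, then SF-MPQ-2, each at 0.05 and confirmatory only if the one before is significant.
2. The within-group paired t-tests are descriptive and cannot support a claim of effectiveness.

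If the three scales must stay equal, replace item 1 with one of the following:

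- Holm: smallest P against 0.05/3 = 0.0167, the next against 0.025, the largest against 0.05, stopping at the first failure.
- A rule that all three must reach 0.05.

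Each option needs wording only, with no added patients or data. The costs in power differ:

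- **Fixed order:** none for the Tampa scale, but the pain scales lose confirmatory status if it fails.
- **Holm:** a scale with 80% power at 0.05 has Φ(2.802 − 2.394) = Φ(0.408), about 66%, at the first step.
- **All three required:** with 80% power on each scale, joint power is 0.8³ = 51% if independent, 61% at r = 0.5 and 72% at r = 0.9.
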